3. INVESTIGATIONAL PLAN

3.1 Study Design

This is a multi-center, OLE study for patients with DS or LGS who have previously participated in double-blind, placebo-controlled, clinical studies of GWP42003-P (the core studies, as detailed in [Table 1](#)). This study consists of a 2-week titration period and a maintenance period followed by a 10-day taper period.

3.1.1 Titration Period

When patients have completed the core study from which they enter this study, they may either be receiving Placebo (of varying dose), 5 mg/kg/day GWP42003-P, 10 mg/kg/day GWP42003-P or 20 mg/kg/day GWP42003-P as per their original allocation in their respective core study. Upon entering this study, patients will titrate to 20 mg/kg/day

GWP42003-P using a recommended titration schedule during the 2-week titration period to achieve a stable dose prior to entering the maintenance period.

3.1.2 Maintenance Period

Patients will continue dosing at 20 mg/kg/day GWP42003-P during the maintenance period. However, Investigators may decrease the dose if the patient experiences intolerance, or increase the dose if required for better seizure control, until the optimal dose is found. The Investigator may schedule additional clinic visits to facilitate dose adjustments, e.g. when increasing doses above 20 mg/kg/day GWP42003-P. Patients whose dose has been decreased can have their dose increased again provided there is adequate tolerance. The maximum dose allowed during this study is 30 mg/kg/day GWP42003-P. If seizure freedom is achieved with use of GWP42003-P during the study, the Investigator should consider reducing the dose of concomitant AEDs after six months of seizure freedom.

3.1.3 Study Completion and Taper Period

If market authorization is granted for GWP42003-P (in DS or LGS) or after a maximum period of time receiving treatment, depending on the country in which the patient enrolls, (whichever occurs first), the patient will complete the study. Patients who do not immediately continue to use GWP42003-P will then commence a taper period (down-titrating 10% per day for 10 days) and complete an 'End of Taper Period' visit followed by a Follow-up visit (can be by telephone) four weeks later. If a patient opts not to continue with GWP42003-P treatment, they will commence the 10-day taper period and complete the 'End of Taper Period' visit and the Follow-up visit. If supported by the safety data, the Sponsor will look to extend the duration of this study.

3.2 Definition of Sample Size

As this is an open label safety study, there is no formal sample size calculation. All patients who wished to continue on IMP from the populations included in the double-blind Phase II and Phase III core studies in DS and LGS were eligible for inclusion.

3.3 Safety and Efficacy Endpoints

The safety and efficacy endpoints for this SAP are detailed in the following sections.

3.3.1 Primary Endpoint

The safety of GWP42003-P will be assessed by the AE profile and by evaluating changes in the following, relative to the pre-randomization baseline of the Core Study:

- Vital signs.
- Physical examination (including height and body weight).
- 12-lead electrocardiogram (ECG).
- Columbia-Suicide Severity Rating Scale (C-SSRS) score.
- Cannabis Withdrawal Scale (CWS) score or Pediatric Cannabinoid Withdrawal Scale (PCWS) score, as appropriate.
- Clinical laboratory parameters.

The CWS will be administered to patients aged 18 and older while the PCWS will be administered to patients aged 4–17 (inclusive).

The Children's C-SSRS will be used for patients aged 6–18 (inclusive) and the C-SSRS will be used for patients aged 19 and older.

3.3.2 Secondary Endpoints

All Patients:

- Change in quality of life as measured with Quality of Life in Childhood Epilepsy (QOLCE) if 18 years of age or younger, or Quality of Life in Epilepsy (QOLIE) if 19 years of age or older, relative to the pre-randomization baseline of the Core Study, if assessed during the Core Study.
- Change in Subject/Caregiver Global Impression of Change (S/CGIC), relative to the pre-randomization baseline of the Core Study.
- Change in adaptive behavior as measured with the Vineland Adaptive Behavior Scales, Second Edition (Vineland-II), relative to the pre-randomization baseline of the Core Study, if assessed during the Core Study.
- Change in the number of inpatient epilepsy-related hospitalizations (number of hospitalizations due to epilepsy in each 28-day period), relative to the pre-randomization baseline of the Core Study.
- Change in the use of rescue medication (number of days used in each 28-day period), relative to the pre-randomization baseline of the Core Study.
- Maintenance of seizure frequency reduction and freedom from seizures during the OLE study.
- Percentage change in the frequency of total seizures, relative to the pre-randomization baseline of the Core Study.
- Number of patients considered treatment responders, defined as those with a $\geq 25\%$, $\geq 50\%$, $\geq 75\%$, or 100% reduction in total seizures, relative to the pre-randomization baseline of the Core Study.
- Number of patients experiencing a $> 25\%$ worsening, $- 25$ to $+ 25\%$ no change, 25 – 50% improvement, 50 – 75% improvement or $> 75\%$ improvement in total seizures, relative to the pre-randomization baseline of the Core Study.
- Percentage change in the frequencies of subtypes of seizures, relative to the pre-randomization baseline of the Core Study.
- Changes in duration of seizure subtypes as assessed by the Subject/Caregiver Global Impression of Change in Seizure Duration (S/CGICSD), relative to the pre-randomization baseline of the Core Study.
- Change in the number of episodes of status epilepticus, relative to the pre-randomization baseline of the Core Study.
- Change in cognitive function as measured with a cognitive assessment battery, relative to the pre-randomization baseline of the Core Study, if assessed during the Core Study.
- Change in growth and development for patients less than 18 years of age by measurement of height, weight, insulin-like growth factor-1 (IGF-1) levels and Tanner Staging (for patients aged 10–17 [inclusive], or earlier if clinically indicated by onset of menarche or other signs of precocious puberty), relative to the pre-randomization baseline of the Core Study.
- Effects on menstruation cycles (in females).
- Drug abuse liability, as measured by AEs of abuse potential, drug accountability and Study Medication Use and Behavior Survey in patients aged 12 and older.

DS Patients Only:

- Percentage change in total convulsive seizure frequency, relative to the pre-randomization baseline of the Core Study.
- Percentage change in total non-convulsive seizure frequency, relative to the pre-randomization baseline of the Core Study.
- Number of patients considered treatment responders, defined as those with a $\geq 25\%$, $\geq 50\%$, $\geq 75\%$, or 100% reduction in convulsive seizures, relative to the pre-randomization baseline of the Core Study.
- Number of patients experiencing a $> 25\%$ worsening, $- 25$ to $+ 25\%$ no change, 25–50% improvement, 50–75% improvement or $> 75\%$ improvement in convulsive seizures, relative to the pre-randomization baseline of the Core Study.

LGS Patients Only:

- Percentage change in the number of drop seizures, relative to the pre-randomization baseline of the Core Study.
- Percentage change in the number of non-drop seizures, relative to the pre-randomization baseline of the Core Study.
- Number of patients considered treatment responders, defined as those with a $\geq 25\%$, $\geq 50\%$, $\geq 75\%$, or 100% reduction in drop seizures, relative to the pre-randomization baseline of the Core Study.
- Number of patients experiencing a $> 25\%$ worsening, $- 25$ to $+ 25\%$ no change, 25–50% improvement, 50–75% improvement or $> 75\%$ improvement in drop seizures, relative to the pre-randomization baseline of the Core Study.

4. STATISTICAL METHODS

4.1 General Considerations

All tables will be presented by indication (where appropriate), including an overall count, as follows:

Dravet Syndrome (N=XX)	Lennox-Gastaut Syndrome (N=XX)	Overall (N=XX)
------------------------	--------------------------------	----------------

In all tables, listings and figures, the study visits will be referred to and labelled as per [Table 2](#)

Table 2 Study Visits

Actual Visit	Visit Label
Visit 1: Day 1	Day 1
Visit 2: Day 15	Day 15
Visit 3: Day 29	Day 29
Visit 4: Day 85	Day 85
Visit 5: Month 6 or Week 24	Week 24
Visit 6: Month 9 or Week 38	Week 38
Visit 7: Week 48 or End of Treatment (only patients who completed at 1 year)*	Week 48
Visit 8: Week 76	Week 76
End of Treatment (only patients who completed on or after Day 400)*	End of Treatment

End of Treatment (withdrawn patients only)	End of Treatment
End of Taper	End of Taper
Post-Taper Safety Call	Post-Taper Safety Call
Safety Follow-Up	Safety Follow-Up

* For some patients, the end of treatment visit occurs after one year in the OLE, whereas for other patients the end of treatment visit occurs after two or more years in the OLE.

Unless stated otherwise, continuous variables will be summarized showing the number of non-missing values (n), mean, standard deviation, median, minimum and maximum and categorical variables will be summarized showing the number and percentage of patients falling in each category. For continuous summaries of seizure frequency, the lower and upper quartiles will also be presented.

Minimum and maximum values will be presented to the same decimal precision as the raw data. Mean and median will be presented to one more decimal place than the raw data, and standard deviation to 2 more decimal places than the raw data. Percentages will be presented to one decimal place.

For patients who enter the OLE on the same day as the core study end of treatment or end of taper visit, the CRF for this study did not require some data to be entered for a second time. Hence, for visit based endpoints, if a patient does not have data entered in this study at Visit 1, then data from the end of treatment or end of taper visit in the core study will be used, provided that the date of collection is on Day 1 of the OLE.

Unless otherwise stated, all summaries will be presented by indication.

All analyses and summaries will be produced using SAS Version 9.4.

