13.1 Sample Size, Power and Significance Levels

As this is an open label safety study, there is no formal sample size calculation. All patients who wish to continue on IMP from the populations included in the double-blind Phase 2 and Phase 3 Core Studies in DS and LGS will be eligible for inclusion. Approximately 680 patients will be enrolled.

All data collected during this study will be summarized across time, using appropriate descriptive statistical methods. There will be no formal hypothesis testing.

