13.6.2.3 Vital Signs, 12-lead Electrocardiogram, Physical Examination and Other Safety Data

Vital signs, ECG and physical examination data will be summarized at baseline (Core Studies), screening (OLE Visit 1) and at each time point during the treatment period using appropriate summary statistics. Changes in the vital signs from baseline (Core Studies) during and at the end of treatment will also be summarized. Study Medication Use and Behavior Survey data will be summarized using appropriate summary statistics.

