4.1.4.2 Last Visit

Last visit for endpoints assessed at clinic visits is defined as the last scheduled visit (not including the end of taper or safety follow-up visits) at which patient's last evaluation is performed.

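### The SAP's End of Treatment row combines all withdrawal visits with the end visits of late completers and sends one-year completers to Week 48, so it represents neither all treated patients nor all completers

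*SAP*

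**What the plan says.** SAP 4.1 makes Table 2 binding on all output: "In all tables, listings and figures, the study visits will be referred to and labelled as per" Table 2. Three of its rows concern the last on-treatment visit:

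- "Visit 7: Week 48 or End of Treatment (only patients who completed at 1 year") carries the label Week 48.
- "End of Treatment (only patients who completed on or after Day 400") carries the label End of Treatment.
- "End of Treatment (withdrawn patients only") also carries the label End of Treatment, whatever the day of withdrawal.

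The footnote confirms that the first group is not empty: "For some patients, the end of treatment visit occurs after one year in the OLE".

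SAP 4.5.1 summarises endpoints on the safety analysis set, that is, all dosed patients. Protocol 13.6.2.2 to 13.6.2.4 promise end-of-treatment change from the Core Study baseline for laboratory data, vital signs and C-SSRS. For vital signs the wording is: "Changes in the vital signs from baseline (Core Studies) during and at the end of treatment will also be summarized".

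SAP 4.1.4.2 offers a possible all-patient summary: "Last visit for endpoints assessed at clinic visits is defined as the last scheduled visit" with an evaluation, excluding the taper and follow-up visits. No endpoint section, and no title in the SAP's list of tables, says where it is reported.

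**The concern.** A reader of a by-visit safety table will take the End of Treatment row in one of three ways: as the end value of everyone treated, as the long-term value in those who finished, or as the state at withdrawal. The label rule delivers none of these. It takes in every withdrawal but only some completers, and time on drug within the row can run from days to the 208-week maximum in Protocol 4.1.

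The tables affected are those built on visits: laboratory, vital signs, ECG, C-SSRS, quality of life, Vineland-II, cognition, S/CGIC, Tanner staging and menstruation. Several of these are components of the primary safety endpoint. Tanner staging and menstruation are the most exposed. SAP 4.5.8.11 and 4.5.8.12 describe only Visit 1 and end of treatment for them, yet a one-year completer's end value is labelled Week 48.

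Withdrawal is partly driven by outcome (Protocol 10 lists transaminase criteria and adverse events), so the two groups sharing the row may well differ in the quantities being summarised.

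**Working it through.** The plan states no figure to reproduce. The check is one of composition.

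**Groups.** Let W be withdrawn patients, C1 one-year completers and C400 completers on or after Day 400.

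- End of Treatment row: W + C400.
- All treated patients: W + C1 + C400.
- All completers: C1 + C400.

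Whenever C1 and W are both above zero, the row equals neither of the other two. This follows from Table 2 and its footnote alone.

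**Share of withdrawals at full attendance.** Let w be the proportion withdrawn and f the share of completers who finish at one year. The documents give neither, so both are assumptions. The withdrawn share of the row is s = w / (w + (1 − w)(1 − f)).

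| w | f = 10% | f = 30% | f = 50% |
|---|---|---|---|
| 20% | 21.7% | 26.3% | 33.3% |
| 30% | 32.3% | 38.0% | 46.2% |
| 40% | 42.6% | 48.8% | 57.1% |

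For example, 0.30 / (0.30 + 0.70 × 0.70) = 0.30 / 0.79 = 38.0%.

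Protocol 13.1 states: "Approximately 680 patients will be enrolled". If all 680 are dosed and 30% withdraw, the row holds 680 × 0.93 ≈ 632, 680 × 0.79 ≈ 537 or 680 × 0.65 = 442 patients at the three values of f.

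**Effect on a mean.** Suppose the two completer groups have the same mean change and withdrawn patients differ from them by D. The row mean then departs from the all-patient mean by (s − w) × D. With w = 30% this is 0.023 D, 0.080 D or 0.162 D. It departs from the completers' mean by s × D, that is 0.323 D, 0.380 D or 0.462 D. Misreading the row as a completers' value is the larger error.

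**Attendance.** Protocol 10 asks for the withdrawal-visit assessments only where possible. If a fraction a of withdrawn patients attend and all completers do, the share becomes a·w / (a·w + (1 − w)(1 − f)). With w = 30% and f = 30%:

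- a = 100%: 0.30 / 0.79 = 38.0%
- a = 80%: 0.24 / 0.73 = 32.9%
- a = 60%: 0.18 / 0.67 = 26.9%

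The share exceeds w only when a is above C400 / (C1 + C400) = 1 − f, here 70%.

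**Does Last Visit repair it?** As an all-patient end value it could, but nothing in the SAP calls for it. Its wording refers to scheduled visits, whereas Protocol 9.2.12 calls the visit for transition to commercial product unscheduled. Whether that visit counts is therefore unclear.

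**The case against.** The strongest reply is that pooling follows the protocol. Section 9.2.12 defines a single End of Treatment/Withdrawal visit, Appendix 1 gives it one column, and 13.6.2.2 asks for the laboratory summary on the safety set, not on completers. Placing one-year completers at Week 48 aligns them with others at a similar time on drug, and the footnote discloses it. The study is descriptive, so no error rate depends on the row. This stands in part: a pooled end-of-treatment row is legitimate in itself. It does not justify a pooled row that leaves out one class of completer, because that is no longer a safety-set summary.

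Four stronger readings are tempting, and the documents do not support them.

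- *One-year completers are dropped.* They are not; their end values appear under Week 48.
- *Withdrawn patients are visible only in this row.* Their earlier visits remain in the earlier rows. Protocol 9.2.13 also schedules vital signs, physical examination and C-SSRS at End of Taper, with ECG and laboratory samples for those who withdraw early and taper.
- *Liver-related or AE-related withdrawals are hidden.* The Hy's Law table (SAP 4.5.3.1), the tables of at least one flagged vital sign or ECG value, the summary of TEAEs leading to discontinuation and the abnormal-laboratory listings do not use this row. Nor do the 12-week seizure periods in SAP 4.5.9.
- *Withdrawals are certainly over-weighted.* That depends on attendance, as shown above.

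It is also fair to say that the one-year group may be small. The current protocol has no one-year completion route, and SAP 3.1.3 refers only to a country-dependent maximum. With f at 10%, the share moves only from 30% to 32.3%.

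**Conclusion.** The point holds as a mislabelled population in visit-based tables. By the SAP's own rule, the End of Treatment row is neither all treated patients nor all completers, and the one definition that could supply an all-patient end value is not assigned to any table. That conclusion needs no assumption beyond the existence of one-year completers, which the SAP confirms, and of withdrawals.

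The amount and direction of any distortion are not established. If withdrawn patients attend about as often as completers, the row over-represents them. The illustrative excess runs from about 2 to 17 percentage points over the assumed ranges (21.7 − 20 = 1.7 at the low end, 57.1 − 40 = 17.1 at the high end). At low attendance the row under-represents them instead. The change is worth making because the protocol promises end-of-treatment summaries for primary safety measures, but no test or decision rule depends on it.

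**What to change.** In SAP Table 2, replace the shared label by two: **Withdrawal visit**, for withdrawn patients, and **End of Treatment – completers**, for all completers. Put the one-year completers' end visit in the completers row as well as in Week 48, with a footnote. State how a completion after the one-year visit but before Day 400 is labelled, since Table 2 does not say.

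Add an all-patient row based on Last Visit to each visit-based table. Reword SAP 4.1.4.2 so that the unscheduled End of Treatment visit counts. That row would also bring in the last available on-treatment evaluation of withdrawn patients who missed the withdrawal visit.

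The cost is SAP wording, one more visit label, one added row in the visit-based tables, and one group of patients shown in two rows. No new data are needed.

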4.1.1.1 Choice of Baseline

For all visit-based endpoints, change from baseline will be calculated with reference to the core study baseline only.

For seizure-related endpoints, percentage change from baseline will be calculated from the core study baseline period.

4.1.2 Handling of Missing Data

4.1.2.1 Seizure Data

If a patient withdraws during the time after which they have taken their first dose in the OLE, then seizure frequencies will be calculated from all the available data prior to the patient withdrawing.

Last observation carried forward (LOCF) methodologies that will be carried out on seizure data are discussed in Section 4.5.9.

4.1.2.2 Adverse Events

Missing and/or incomplete dates/times for AEs will be imputed in a manner resulting in the earliest onset or the longest duration during the treatment period, taking into account that the start date/time should not be after the stop date/time. Stop dates/times will not be imputed if the AE is ongoing.

The imputation method will only be used to determine treatment emergence, time to first onset of AE and time to AE resolution, and imputed dates/times will not be presented in AE outputs.

A worst-case approach will be followed in the event of missing severity or causality data. If the severity is missing, 'Severe' will be imputed. If causality data is missing, 'Yes' will be imputed for the question 'Plausible relationship to study medication'.

4.1.2.3 Concomitant Medication

Missing concomitant medication dates will be handled in a similar fashion as described for AEs in Section 4.1.2.2.

4.1.3 Day Numbering

The first day of open label treatment (Day 1) will be the date of Visit 1. Any days prior to Day 1, including visits that occur in the core studies that are referenced in this study, will be numbered relative to this day and calculated as:

$$\text{Date} - (\text{Date of Day 1})$$

to give Day -1, -2, -3 etc.

Any days post Day 1 will be calculated as:

$$1 + \text{Date} - (\text{Date of Day 1})$$

4.1.4 Definitions

4.1.4.1 Core Study Baseline

For interactive voice response system (IVRS) based endpoints, the core study baseline will include all available data prior to Day 1 of the core study as per the derivation in the core study.

For visit based endpoints, the core study baseline will be the visit that was assigned as baseline in the core study. No re-derivation will be carried out.

4.1.4.2 Last Visit

Last visit for endpoints assessed at clinic visits is defined as the last scheduled visit (not including the end of taper or safety follow-up visits) at which patient's last evaluation is performed.

4.1.4.3 Last 12 Weeks

The last 12 weeks (84 days) for IVRS based endpoints is defined as all available data from 12 weeks prior to the earliest of the date of the patient completing/withdrawing from the study, the last call to IVRS, or the last dose date as recorded on the "End of Treatment Study Outcome" page of the CRF.

4.1.4.4 Total Seizures

Total seizures are defined as the combination of convulsive and non-convulsive seizures.

4.1.4.5 Drop Seizures (LGS Patients Only)

Drop seizures are defined as the subset of tonic-clonic, tonic or atonic seizures that are reported as drop seizures in IVRS.

4.1.4.6 Convulsive Seizures

Convulsive seizures are defined as tonic-clonic, tonic, clonic or atonic seizures.

4.2 Analysis Sets

There will be one analysis set.

4.2.1 Safety Analysis Set

The safety analysis set will be defined as all patients who receive at least one dose of IMP in the study. Only patients for whom it has been confirmed that they did not take any IMP will be excluded.

4.3 Listings

All data will be listed and ordered by core study, site, core study treatment, patient number and, where appropriate, chronological order of assessment. Listings will be created for each of the subsequent sections of the SAP.

Visit dates need not be included on all of the listings, but day numbers will be included, where appropriate.

Other derived variables (e.g. changes from core study baseline values) that are calculated for analysis purposes or to aid interpretation of the data will be added to the listings as appropriate.

